## **7. Study Withdrawal**

A) Discontinuation of participation of the patient due to withdrawal of consent

B) Discontinuation of participation due to:

- a) disclosure of exclusion criteria after enrolment;
- b) occurrence during participation in study of a serious new clinical event which contraindicates vasodilatation, e.g. acute stroke, acute traumatic brain injury with cerebral edema;
- c) decision of the treating medical team to switch towards palliative care

If there are findings that indicate that a further participation in the study would lead to a disproportionate risk for the patient’s health or life, the patient may be excluded from the study.

In case of an adverse event or a serious adverse event (e. g. symptomatic hypotension, acute coronary syndrome, acute kidney injury etc.) or known or unexpected side effects related to the study medication the treatment with the concerning medication will be adjusted or suspended. All other procedures remain unaffected and the patient will not be excluded from the study.

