### **8.2 Statistical Analysis**

The statistical analyses will be performed using the SPSS / PC (version 14.0, SPSS Inc., USA) software package. A statistical significance level (p-value) of 0.05 will be used. All data will be analyzed on an intention-to-treat basis. Comparisons will be made using the t-test, Mann Whitney U-test, Fisher's exact test, survival analysis (Kaplan Meier method), Cox regression analysis and chi-square test as appropriate. All hypothesis testing will be two-tailed. Statistical support will be performed by [name] from the Institute of Social and Preventive Medicine of the University of Basel.

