### **f. Sample size**

Sample size calculation is based on the on the data from the BASEL V study. A hypothesized 20%-decrease of the composite endpoint death or HF re-hospitalization at 180 days, will require 385 patients per treatment arm to obtain, with a probability of 80%, a log rank test result that is statistically significant at the 5%-level. In order to compensate for an expected 1-2% of patients in whom the primary endpoint could not be assessed at 180 days due to loss to follow-up or complete withdrawal of ICF, it was planned to enroll approximately 780 patients.

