### **m. Intention- To -Treat (ITT)**

The intention to treat population consists of all patients randomized. The primary and secondary endpoints of patients randomized to early goal-directed decrement of preload and afterload (intervention group) will be compared to the patients randomized to standard of care by the intention-to-treat principle.

Patients without a follow-up assessment at 6 months for the primary endpoint will be censored at the time of the last follow-up information available.

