**v. Use of efficacy subset**

All patients will be analyzed by intention-to-treat and reported according to their randomized arm, irrespective of whether and how much of the study drug they received. Note that the last assessment of the endpoints will be used if otherwise no measurement of the endpoint could be conducted at 180 days, due to withdrawal of consent or due to lost to follow-up incl. failure to collect all the required documents for endpoint adjudication.

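### Protocol section 7 B ends participation for late-found exclusions, stroke-type events and palliative care without saying that death and HF readmission are still collected to day 180

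*Combined protocol and SAP*

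**What the plan says.** **Protocol, 7. Study Withdrawal.** Part A covers withdrawal of consent. Part B ends participation for three further reasons: (a) exclusion criteria that come to light after enrolment; (b) "occurrence during participation in study of a serious new clinical event which contraindicates vasodilatation", with stroke and brain injury as examples; (c) "decision of the treating medical team to switch towards palliative care". A and B use the same term, the ending of participation. The section then treats other adverse events differently. There, the medication concerned is adjusted or suspended, everything else carries on, and the patient stays in the study.

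**Primary endpoint** (Protocol 2.1, SAP 2.1). Death or HF re-hospitalisation to 180 days.

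**SAP, Intention-To-Treat (5.3 in the contents).** The set is all randomised patients. "Patients without a follow-up assessment at 6 months for the primary endpoint will be censored at the time of the last follow-up information available".

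**SAP, Use of efficacy subset (6.6.5).** "the last assessment of the endpoints will be used if otherwise no measurement of the endpoint could be conducted at 180 days". The reasons named are withdrawn consent and loss to follow-up, and the latter includes missing adjudication documents.

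**SAP, Assessment of objectives (2.3).** Patients are contacted at 90, 180 and 360 days. Family physicians, chart review and the national mortality registry are further sources. A blinded committee adjudicates on all the information available.

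**SAP, Adverse events (11.1).** All SAEs are collected for the first 180 days; death is on the SAE list.

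**SAP, Blinding (3.4).** Hospital physicians and patients are not blinded. Physicians responsible for care after discharge are.

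**The concern.** A switch to palliative care and an acute stroke both signal a raised risk of death, and death is a component of the primary endpoint. If outcome collection stops at that moment, the reason for censoring is tied to the outcome. Cox and log-rank analyses assume that it is not.

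Two features of this trial make that matter more. The in-hospital decision is taken by a team that knows the arm. And Protocol section 6 names hypotension with reduced organ blood flow as the main potential harm of the intervention, so discontinuations under (b) or (c) could differ between arms for causal reasons as well. In that case the arm with more discontinuations would lose more of its deaths. Keeping every randomised patient in the intention-to-treat set does not help if outcomes are no longer obtained.

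**Working it through.** **1. What happens to a 7 B patient, step by step**

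- Does section 7 end follow-up? It ends participation, and it withholds from group B the assurance it gives for other adverse events. A site could reasonably stop the telephone contacts.
- Does another section restore follow-up? SAP 2.3 and 11.1 describe contacts, registry checks and SAE collection in general terms. Neither mentions patients discontinued under section 7.
- What does the analysis do without a 180-day assessment? SAP 5.3 censors at the last information, whatever the reason. SAP 6.6.5 names other reasons, so it applies only if a 7 B patient is classed as lost to follow-up.
- Is this within the SAP's allowance? SAP 3.2 expects 1-2% unassessable, from loss to follow-up or complete withdrawal of consent. 7 B discontinuation is not among the reasons.

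**2. The plan's own figure, to set event rates**

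Inputs: "A statistical significance level (p-value) of 0.05 will be used"; "All hypothesis testing will be two-tailed" (both Protocol 8.2); "with a probability of 80%, a log rank test result that is statistically significant at the 5%-level" and a "hypothesized 20%-decrease of the composite endpoint death or HF re-hospitalization at 180 days" (SAP 3.2). The control event rate p is not given.

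Reading the decrease as relative, HR = ln(1 − 0.8p) / ln(1 − p), and events = 4(1.960 + 0.842)² / (ln HR)².

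- At p = 0.50: HR = ln 0.60 / ln 0.50 = 0.737, events = 338, and 338 / (2 × 0.45) = 376 per arm.
- The Freedman formula gives 381 and two proportions give 388.
- The stated 385 corresponds to p = 49.3%, 49.7% or 50.2% under the three methods.

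So 50% versus 40% fits the plan but is an assumption. It implies 385 × (0.50 + 0.40) = 346.5 events.

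**3. Illustration if follow-up stops**

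Assumed, not in the documents: a share d of an arm is discontinued under 7 B, 90% of these patients die by day 180, and none of those deaths is recovered.

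- Held as event-free: observed risk r = p − 0.9d.
- Censored early (SAP 5.3): r = (p − 0.9d) / (1 − d).
- Observed HR = ln(1 − r₁) / ln(1 − r₀), with subscript 1 for intervention and 0 for control.

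No true effect, p = 0.45 in both arms:

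| Discontinued (intervention vs control) | Held as event-free | Censored early |
|---|---|---|
| 4% vs 2% | r 0.414, 0.432; 0.5344 / 0.5656 = 0.945 | r 0.4313, 0.4408; 0.5643 / 0.5813 = 0.971 |
| 5% vs 2% | r 0.405, 0.432; 0.5192 / 0.5656 = 0.918 | r 0.4263, 0.4408; 0.5557 / 0.5813 = 0.956 |
| equal, e.g. 3% vs 3% | 1.00 | 1.00 |

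True HR 0.737 (40% vs 50%) with 4% vs 2% discontinued: held as event-free, 0.4526 / 0.6578 = 0.688; censored early, 0.4767 / 0.6770 = 0.704.

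If control had the larger share (2% vs 4%), the null HR would move the other way: 1 / 0.971 = 1.03, or 1 / 0.945 = 1.06.

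Equal discontinuation costs events. At 3% per arm, 770 × 0.03 × 0.9 = 20.8 deaths are lost, 6.0% of 346.5. With power = Φ(√E/2 × |ln HR| − 1.96) and HR held at 0.737, power falls from 81.1% (E = 346.5) to 78.6% (E = 325.7).

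**The case against.** A reader might infer that these deaths leave the primary endpoint by rule. The documents do not say that. No section states that 7 B patients are censored or counted as event-free, and the last-assessment rule in SAP 6.6.5 names neither palliative care nor stroke. The per-protocol definition (SAP 5.4 and its footnote) removes patients with late-found exclusion criteria separately from requiring a 180-day assessment. That suggests such patients can still have one. These patients also need not be near death, so the argument about risk rests on (b) and (c).

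A reader might also infer that SAP 5.3 and 6.6.5 contradict each other. For a time-to-first-event endpoint, using the last assessment and censoring at the last information can be the same operation. The wording is loose, but no contradiction is shown. Nor is it established that an incompletely documented event reverts to event-free, because SAP 2.3 has the committee use everything available.

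Deaths have routes that need no patient contact: family physician, charts, registry and SAE reports. Physicians caring for patients after discharge are blinded. The illustration uses invented rates, averaging 3% or more, whereas the SAP expects 1-2% unassessable from its named causes. Its distortion under no true effect comes wholly from the assumed imbalance.

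All of this limits the likely size. What stands is that none of it says follow-up continues after a 7 B discontinuation. The listed sites lie in nine countries and registry access in each is not stated. A mortality registry does not capture HF readmission. Multiple imputation (SAP 10.1.5) is a sensitivity analysis whose listed predictors are baseline characteristics and earlier endpoint status, not the reason for leaving.

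**Conclusion.** Section 7 B is wrong as written, on the condition that sites act on it and stop follow-up. It ends participation for patients of whom some are at high risk of the primary endpoint, and no text secures their outcomes to day 180. If follow-up does stop, SAP 5.3 produces informative censoring unless another source happens to supply the event.

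The size cannot be fixed from the documents. Under the assumptions shown, with more discontinuations in the intervention arm, a null hazard ratio would appear as 0.96 to 0.97 with early censoring and 0.92 to 0.95 if the patients are held as event-free. These are unfavourable cases, since no death is recovered. With equal discontinuation the null hazard ratio stays at 1.00 and the cost is lost events and some power.

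This should be corrected because it touches the primary endpoint and outcomes never collected cannot be restored by analysis. It does not by itself show that the primary analysis is invalid.

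**What to change.** 1. **Protocol 7 B.** Reword so that these three reasons bear only on protocol-directed treatment and do not end outcome follow-up. The 90-, 180- and 360-day contacts, chart review and registry checks continue for every randomised patient except those who withdraw consent to follow-up. This concerns data collection only and asks for no change in clinical care.
2. **SAP 5.3 and 6.6.5.** Replace with one rule for the primary endpoint: time to first event, censored at the last date known alive and event-free. Say that the blinded committee decides on all available information, as SAP 2.3 already provides, so that an incompletely documented event is not reset to event-free.
3. **Patients already discontinued under 7 B.** Retrieve vital status and HF readmission through the sources in SAP 2.3, as far as consent allows. Report 7 B discontinuations by arm and reason.

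The cost is a short protocol clarification, one SAP paragraph, and retrieval work for patients already discontinued. The contacts and data sources are already planned. If the sponsor always meant to follow these patients, the first two changes only put that in writing.

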## **8. Data Management and Statistics**

### **8.1 Data Management and Monitoring**

To appropriately describe the patient population, a dedicated case report form (CRF) including detailed patient history, physical examination, vital parameters during hospitalization and adverse events will be completed. Cost data will be converted in US dollar using the exchange rate of February 1st, 2009. All relevant data will be entered into SecuTrial® (interActive Systems GmbH, Berlin Germany) and Microsoft® Access® 2010 (Version 14.0.7162.5001, Microsoft®, USA). The use of these data is restricted to scientific purposes. Data management and monitoring support will be provided by the Clinical Trial Unit of the University Hospital Basel.

### **8.2 Statistical Analysis**

The statistical analyses will be performed using the SPSS / PC (version 14.0, SPSS Inc., USA) software package. A statistical significance level (p-value) of 0.05 will be used. All data will be analyzed on an intention-to-treat basis. Comparisons will be made using the t-test, Mann Whitney U-test, Fisher's exact test, survival analysis (Kaplan Meier method), Cox regression analysis and chi-square test as appropriate. All hypothesis testing will be two-tailed. Statistical support will be performed by [name] from the Institute of Social and Preventive Medicine of the University of Basel.

### **8.3 Power and Sample Size of the Trial**

Based on the data from the BASEL study (31), a hypothesized 20%-decrease of the composite endpoint death or HF re-hospitalization at 180 days, will require 385 patients per treatment arm to obtain, with a probability of 80, a log rank test result that is statistically significant at the 5%-level.

## **9. Study Schedule**

- Recruitment of first patient: November 10th, 2007
- Recruitment of last patient: if n = 770
- 180 day follow up complete: n = 770 + 180 days
- 360 day follow up complete: n = 770 + 360 days (last visit last subject)
- Main manuscript submission: n = 770 + 540 days

## **10. Regulatory Considerations, Ethical Review, Confidentiality Informed Consent and Liability**

### **10.1 Regulatory Considerations**

This study will be conducted in accordance with the ethical principles stated in the most recent version of the Declaration of Helsinki or the applicable International Conference on Harmonization (ICH) guidelines on good clinical practice, whichever represents the greater protection of the individual.

### **10.2 Ethical Review**

This protocol will be submitted for approval by the conjoined local ethic committee of the Northwestern and Central part of Switzerland, respectively the competent local ethic committees or IRBs for all other participating sites.

### **10.3 Confidentiality**

All medical records and data are bound to professional discretion and will be kept in confidence. Data will be organized, managed, and stored in a password protected software database and only study team members and the ethical committee will be able to access them. No data will be sent over the internet unless it is de-identified.

### **10.4 Informed Consent**

Patients will be asked to give written informed consent before study entry. They will agree on the use of their data for scientific purposes. The informed consent document will be used to explain in simple terms the aim of the study, and required procedures. The informed consent document contains a statement that the consent is freely given, and that the patient is free to withdraw from the study at any time.

### **10.5 Liability**

Diagnostic and therapeutic procedures in this clinical trial are covered by liability insurances. Study subjects at centers in Switzerland are insured by the University Hospital Basel with Zurich Versicherungen AG. For centers outside Switzerland, the coverage will be organized by the sponsor when possible. Alternatively, the participating center will seek and -previously approved by the sponsor - hire an insurance policy whose cost will be reimbursed by the sponsor.

### **10.6 Definition and Reporting of Adverse Events**

According to the Federal Law on Medicinal Products and Medical Devices (Law on Therapeutic Products - LTP) and the Federal Law on Clinical Trials with Medicinal Products (VKlin) the following predefined events that occur during trial period must be recorded and reported to the authorities:

- Adverse Events (AE)
- Serious Adverse Events (SAE)

- Suspected Unexpected Serious Adverse Reaction (SUSAR)

### **10.6.1 Definition of Adverse Events according to the International Conference of Harmonization (ICH)**

An **Adverse Event (AE)** is any untoward medical occurrence in a patient or clinical investigation subject, who has been administered a pharmaceutical product, which does not necessarily have a causal relationship with this treatment. An adverse event can therefore be any unfavorable and unintended sign (including an abnormal laboratory finding), symptom, or disease temporally associated with the use of a medicinal (investigational) product, whether or not related to the medical (investigational) product.

A **Serious Adverse Event (SAE)** means an adverse event that requires either in-patient hospitalization, prolongation of existing hospitalization, is a congenital anomaly / birth defect, results in persistent or significant disability or incapacity, is life threatening, or results in death.

A **Suspected Unexpected Serious Adverse Reaction (SUSAR)** is defined as a serious adverse event / drug reaction, the nature or severity of which is not consistent with the applicable product information (e.g. Investigators Brochure for an unapproved investigational medicinal product).

### **10.6.2 Reporting of Adverse Events**

AEs must be recorded by clinical investigator using the predefined section of the case report form. Annually, the sponsor reports every adverse event to Swissmedic (Swiss Agency for Therapeutic Products).

In case of SAE, the clinical investigator must inform the sponsor within 24 hours by fax or telephone using a predefined SAE reporting formulary. Furthermore the clinical investigator must report life-threatening SAE to the responsible institutional review board (IRB) or institutional ethical committee (IEC) in written form within 7 days. All other serious adverse events must be reported by the clinical investigator to the IRB / IEC within 15 days.

Life-threatening serious adverse events that fulfil the definition of a SUSAR must further be reported by the sponsor to Swissmedic using the Council for International Organization of Medical Sciences (CIOMS) formulary within seven days. The reporting deadline for all other SUSARS to Swissmedic is 15 days. Furthermore, all participating institutes have to be informed immediately by the sponsor about SUSARs. As deaths or HF rehospitalizations are part of the primary endpoint, these events will only be reported to Swissmedic in the annual AE report.

## 1. Study synopsis

In contrast to treatment for chronic heart failure (HF), which is based on several large prospective randomized controlled trials, treatment for acute heart failure is largely based on uncontrolled studies, clinical experience and expert opinion. Perhaps at least in part related to the uncertainties in the treatment of acute heart failure, outcome of patients with acute heart failure is extremely poor with mortality arising to 50% at three years. As more than 85% of patients with acute heart failure are treated in the non-ICU / CCU setting - the Emergency Department and the regular medical ward-, it is still notable that appropriate treatment is particularly ill-defined in this setting.

Based on the aforementioned premise, our aim is to test the hypothesis that a comprehensive approach using an early goal-directed therapy with a target systolic blood pressure of 90 to 110 mmHg by aggressive vasodilatation in patients with acute heart failure in the non-ICU setting, is safe and has the potential to more rapidly improve dyspnea, to more rapidly and more extensively reduce heart failure disease severity as quantified by B-type natriuretic peptide levels and most importantly to reduce the occurrence of death and heart failure readmission. Due to the high cost associated with hospitalizations for heart failure, our study has the potential to define a novel treatment strategy that might also significantly reduce the treatment cost associated with acute heart failure.

This trial was designed as a prospective, randomized, controlled multicenter study aimed to enroll 770 patients presenting with acute heart failure at the emergency departments at the participating study sites. Patients will be randomly assigned 1:1 after stratification for site and B-type natriuretic peptide (BNP, NT-proBNP) levels to an early goal-directed therapy or standard care according to current guidelines. Early goal-directed therapy aims to aggressive vasodilatation by using sublingual and transdermal nitrates, hydralazine (to avoid tolerance to nitrates) and rapid up-titration of angiotensin converting enzyme inhibitors and angiotensin II receptor blockers with a target systolic blood pressure of 90 mmHg to 110 mmHg. Timing and dosing of diuretics and all other treatments are left to the discretion of the treating physician in both groups. The primary endpoint is death or heart failure readmission within 180 days. Secondary endpoints include the quantitative assessment of dyspnea, need for admission to the intensive care unit, surrogate markers like BNP or NT-proBNP, the digitally recorded third heart sound, renal function, time to discharge, functional status and quality of life, falls, total treatment cost, and cost-effectiveness. Patients will receive extensive clinical and economic follow-up of at least 360 days. A clinical endpoint committee blinded to group assignment will adjudicate endpoints.

## 2. Study objectives

### a. Primary objective

The aim of our study is to determine the safety and efficacy of an early goal-directed preload and afterload decrement with a target systolic blood pressure of 90 mmHg to 110 mmHg by aggressive vasodilatation versus standard medical care in a non-ICU setting in patients with acute HF. The primary endpoint is **death or heart failure re-hospitalization** up-to 180 days of follow-up.

### b. Secondary objectives

Secondary endpoints are:

- All-cause mortality at 180 days.
- HF re-hospitalization at 180 days.
- Death or re-hospitalization from all causes at 180 days.
- Need for ICU admission during initial hospitalization.
- Acute coronary syndrome during initial hospitalization.
- Symptomatic hypotension during initial hospitalization.
- B-type natriuretic peptide (BNP) and creatinine level at 48 h and at discharge.
- Changes in circumferences of both legs and central venous pressure during hospitalization.
- Change in patient-assessed dyspnea at 48 h and prior to discharge.
- Blood pressure course over the first 6 days.
- Time to disappearance of a third heart sound (if present initially).
- Time to discharge.
- In-hospital days for HF at 180 days and 360 days.
- Total treatment cost at 180 days and 360 days.
- Functional status at 180 days and 360 days.
- Quality of life (EQ-5D-3L) at 180 days and 360 days.
- Fractures due to falls within 180 days and 360 days.
- Death or HF re-hospitalization at 360 days.

